We will measure TNFR expression by B cells following immunization with PCV13 in 65-75 year old RT and compare them to each of the groups described in Specific Aim 1. Gene expression, with focus on the B cell activating factor (BAFF) system, will be measured in PPS-specific and non-PPS specific B cells using single cell genomics and flow cytometry. These measures will be correlated with post-immunization functional antibody activity, a surrogate of protection.

Our central hypothesis is that the aging RT population responds poorly to PCV13 vaccination reflecting the combined effects of aging and RT. We postulate that both the number of memory B cells and expression of tumor necrosis factor (TNF) superfamily receptors, which play crucial roles in the response to pneumococcal polysaccharides (PPS), are deficient in the elderly RT population and contribute to poor pneumococcal vaccine responses.

We have developed fluorescently labeled PPS allowing us to study the nature and surface receptors of PPS-specific B cells. Our preliminary data demonstrate that RT recipients 1. Respond poorly to pneumococcal immunization as measured by antibody titer and functional antibody activity. 2. RT recipients and healthy elderly have lower absolute number of both IgM and switched memory B cells. 3. The number of PPS-specific IgM and switched memory B cells are significantly lower in RT recipients and 4. TACI and BAFF-R, members of the TNF superfamily receptors, expression is significantly lower in the PPS-specific memory B cells in the RT population versus healthy controls. The overall objective of this proposal is to characterize the immune response and explore possible mechanisms of poor vaccine responsiveness following immunization with PCV in the rapidly growing group of elderly with RT. As the RT population is a

heterogeneous group we will study only those in whom the underlying cause of renal failure is diabetes mellitus type 2 (DM2) and/or hypertension (HTN).

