certain Toll like receptors (TLR) play a crucial role in the immune response to pneumococcal vaccination [25, 26]. As shown in preliminary data, we have found decreased TACI and BAFFR expression in PPS-specific B cells derived from RT recipients. Although the number of RT recipients studied is very small, it was a consistent finding and merits further study. Adjuvants that specifically upregulate TACI expression, such as CpG-ODN, could therefore effectively increase immune responsiveness to pneumococcal vaccines. This strategy has shown to increase immune and memory responses to the conjugate pneumococcal vaccine in HIV-positive persons [27]. Our central hypothesis is that the elderly RT population responds poorly to PCV13 reflecting combined effects of aging and RT that result in abnormalities in both number of memory B cells and TNF superfamily expression, which play crucial roles in the response to polysaccharide antigens. We will test this hypothesis by measuring PPS-specific antibody and opsonophagocytic antibody responses, PPS-specific B cell phenotypes and surface and gene expression of the TNFR with known role in response to pneumococcal vaccination and correlate these individually with antibody and functional antibody responses. This has important clinical implications as deficient TNFR expression can be modulated by the addition of adjuvants such as CpG-ODN.

Preliminary Data

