4.0 Study Endpoints (if applicable)

The primary endpoint of this study is: quantify the antibody titers in mg/mL and opsonophagocytic antibody titer calculated as serum dilution, number of polysaccharide specific B cells, and absolute number of cells/mL induced by vaccination with PCV13.

Secondary endpoint of the study is to describe differences in gene expression of 56 genes to be determined by single cell PCR and comparing these between groups.

The primary safety endpoint of the study is measured as minimal versus moderate local side effect. Minimal side effect measured as no impairment in activity. Moderate local side effect is a side effect affecting use of the extremity for less than 24 hours.

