10.0 Study Design / Methods

The overall objective of this proposal is to characterize the immune response and explore possible mechanisms of poor vaccine responsiveness following immunization with PCV in the rapidly growing group of elderly with RT. As the RT population is a heterogeneous group we will study only those in whom the underlying cause of renal failure is diabetes mellitus type 2 (DM2) and/or hypertension (HTN). There will be 5 study groups as outlined above.

Volunteers from all 5 study groups will be recruited as above. All individuals from study groups 1-4 who meet the study criteria will receive Prevnar13[®] on day 0. Group 5 volunteers will be recruited during the first year of the study and those who have not previously received PPV23 will receive PPV23 on day 0 and PCV13 on day 366. Blood samples will be obtained as outlined below and results obtained in various groups will be compared.

Timing of blood samples

Peripheral blood samples will be collected at day 0 (pre-immune), day 7, and day 30 (4 weeks post-PPV23) for groups 1-4 and at days 366, 373 and 396 for group 5. In addition, day 5, and 10 blood samples will be obtained from a limited (n=10) number of elderly RT participants to determine the optimal time point for circulation of PPS-specific B cells. Yearly blood samples will be obtained thereafter for serum antibody and OPA analyses to test longevity of antibody and OPA responses. Samples from days 0, 30 and yearly samples will be used for antibody titers and opsonophagocytic assays. Samples from day 0 (day of vaccination with PCV13) and day 7 will be used for flow cytometric analysis. The day 7 time point for isolation of antigen-specific B cells was specifically chosen as we have extensively studied temporal dynamics of antigen-specific B cell in peripheral blood samples (unpublished studies) and have found that the highest number of antigen-specific B cells are present in the peripheral circulation at day 6 and 7 with rapid (70+%) decline at day 8 in healthy young, elderly including those with DM2 and HTN, and HIV-positive. At day 30, a minimal number of PPS-specific B cells were present. Others have described similar findings [28, 29].

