12.0 Data Management

Statistical Analysis Plan and Sample Size Justification for Aims 1 and 2

The primary outcomes in Aim 1 are serum antibody levels and functional antibody response measured using the OPA response at baseline and 30 days post-PVC₁₃ vaccine measured in the five groups defined in Table 1. The primary outcomes in Aim 2 are absolute number and proportion of B-cells phenotype specific to PPS₁₄, 19A, and 23F at baseline and 7 days post-PVC₁₃ vaccine measured in the same five groups. Comparisons between groups and within group between times for each aim will be evaluated using a linear

mixed model (LMM) approach. **The models will include fixed effects for participant group (65-75 RT, 35-45 RT, 65-75 DM/HTN, 65-75 healthy, and 35-45 healthy) and for time (day 0 or 30) and a random subject effect to account for repeated measures of antibody levels within participant.** Model assumptions will be checked graphically and transformations will be considered when necessary. Comparisons for each outcome between groups and within group between times will be evaluated using a series of contrasts from the LMM. **We are presenting power calculations for a range of assumptions to demonstrate that we anticipate having sufficient power to detect observed differences for all comparisons even if we fail to meet the recruitment target.** For power calculations we estimated the effect sizes for sample sizes ranging between 10 to 40 participants per group measured at 2 times at 80% and 90% power using a two-sided test assuming within subject correlation of 0.5 and Bonferroni adjusted and unadjusted significance

Figure 7: Effect sizes for different sample sizes, power, and significance

levels of $p = 0.005$ and 0.05 respectively. We will also evaluate the correlation between serum antibody levels and B cell count with OPA response across all participant groups using an LMM approach where OPA response is the dependent variable and antibody level or B-cell count is the independent variable. The model will include a random subject effect to account for repeated measures in the same subject. We anticipate good correlation (between 0.6-0.99), thus the objective is to estimate the correlation and define the level of precision around that correlation. A sample size of 200 subjects, 40 per group, provides >80% power to detect weak correlations of $r = 0.20$ and allows us to estimate a 95% confidence interval around the correlation to within ± 0.14 .

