Statistical Analysis Plan and Sample Size Justification for Aim 3

Aim 3 will examine differences in expression of TNFR markers (TACI, BCMA, and BAFF-R) using single cell qPCR on a subset of 10 participants (5 responders and 5 non-responders) from each of the 5 groups described in Aims 1 and 2 evaluated at baseline and 7 days post-vaccination. Single cell qPCR allows us to not only evaluate differences in expression between groups but also allows us to estimate the within subject and within group heterogeneity with great precision. Each participant sample provides between 40-96 viable cells that will be evaluated for gene expression at the single cell level. Relative fold-change in expression between participants who are 65-75 RT, 35-45 RT, or 65-75 DM/HTN with respect to the relevant controls will be evaluated using a linear mixed model approach. The model will include fixed effects for participant group, response status, and time and a random subject effect to account for repeated measurements resulting from individual cells from the same subject samples. Comparisons of number of gene expression between groups and within group between times will be evaluated using a series of contrasts from the LMM. For comparisons within group between responders and non-responders, a sample size of 5 responders and 5 non-responders with ≥ 40 cell level measures at 2 time points provides 80% power to detect 2.7 fold-increase or a 0.60 fold-decrease in expression using a two-sided test assuming within subject correlation of 0.5 and a Bonferroni corrected significance level (up to 10 comparisons) of $p = 0.005$. For comparisons between groups, we will have 10 subjects per group allowing us to detect even smaller fold-changes in expression.

All electronic data will be kept on the VA secure V drive or R drive and on MUSC secure Z drive that only team members will have access to.

13.0 Provisions to Monitor the Data to Ensure the Safety of Subjects (if applicable)

All adverse events (AE) will be reported and monitored through the data safety monitoring plan. The AE's will be characterized by: intensity/severity; expectedness; relatedness; frequency; outcome; treatment or action taken.

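### Aim 3 promises to relate TNFR and gene expression to functional antibody activity, but no specified model relates expression to the OPA titre; the only response term is an undefined two-level status

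*Combined protocol and SAP*

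**What the plan says.** The promise appears twice. Section 1.0, under Aim 3, says of TNFR and gene expression: "These measures will be correlated with post-immunization functional antibody activity, a surrogate of protection". Section 2.0 says the measures, TNFR expression among them, will be related to response one by one: "correlate these individually with antibody and functional antibody responses".

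Functional activity is a graded quantity. Section 4.0 lists it as "opsonophagocytic antibody titer calculated as serum dilution", and Section 10.0 schedules it: "Samples from days 0, 30 and yearly samples will be used for antibody titers and opsonophagocytic assays".

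Section 12.0 then gives two relevant models.

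- **Aims 1 and 2.** A mixed model in which "OPA response is the dependent variable and antibody level or B-cell count is the independent variable". TNFR expression is not among the predictors.
- **Aim 3.** Single-cell qPCR on "a subset of 10 participants (5 responders and 5 non-responders) from each of the 5 groups described in Aims 1 and 2", analysed thus: "The model will include fixed effects for participant group, response status, and time and a random subject effect". The within-group responder contrast, "with ≥ 40 cell level measures at 2 time points", is given 80% power for a 2.7 fold-increase or a 0.60 fold-decrease, two-sided at 0.005.

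No section says which assay, serotype, threshold or day makes a participant a responder, or how the five of each kind are picked.

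**The concern.** The link between receptor expression and functional response is the mechanistic part of Aim 3. As written, response enters the analysis only as a two-level label whose basis is not stated. There are two possibilities.

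- **The label is not derived from OPA** (serum antibody is an obvious alternative). Then the link to functional activity is absent from every specified model.
- **The label is a cut of OPA.** Then differences in titre within each class are not used. A participant just over the cut counts the same as the strongest responder.

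Only 10 people per group have single-cell data. Many cells per person do not add information on how OPA varies between people. The analysis would also return a two-class difference rather than the graded relation that Section 1.0 describes.

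**Working it through.** **1. The plan's own figures.** Alpha is 0.05/10 = 0.005, as stated. For 5 v 5 by the normal formula, the detectable standardized difference is d = (z₀.₉₉₇₅ + z₀.₈₀)·√(2/5) = (2.807 + 0.842) × 0.632 = 2.31; with the t distribution on 8 df it is 3.08. The 80% cannot be reproduced because no SD is given. By the normal formula, 2.7-fold implies a log-scale SD of ln 2.7/2.31 = 0.43, and 0.60-fold implies |ln 0.60|/2.31 = 0.22. In any case the figure concerns the responder contrast, not a relation with OPA.

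The correlation figure for Aims 1 and 2 does reproduce: n = 200 and r = 0.20 give 81% power, with a half-width of 0.14. No comparable figure is given for expression against OPA.

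**2. What each model covers.**

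| Model (Section 12.0) | OPA titre in it? | TNFR expression in it? |
|---|---|---|
| OPA on antibody level or B-cell count | Yes, continuous | No |
| Aim 3 expression model | No (response status only) | Yes |

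No row has both. This result needs no assumption.

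**3. Cost of the two-level term if it is an OPA cut.** Assumptions: log OPA response is normal, mean expression per subject is linear in it with correlation r, 40 per group are available, and 5+5 are assayed. The documents give no r for expression.

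A median split of a normal variable multiplies the correlation by √(2/π) = 0.798. By Fisher's z, power = Φ(atanh(r)·√(n−3) − 2.807). With n = 50 and r = 0.5:

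- continuous: 0.549 × 6.856 − 2.807 = 0.96, power 83%;
- cut: r = 0.399, 0.422 × 6.856 − 2.807 = 0.09, power 54%.

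Simulation with group adjustment (within-group-centred regression, two-sided alpha 0.005) agrees:

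| Setting | Cut | Continuous | Difference |
|---|---|---|---|
| Five groups, random 5+5, r = 0.5 | 53% | 81% | 28 points |
| Five groups, random 5+5, r = 0.6 | 79% | 97% | 18 points |
| Five groups, random 5+5, r set for about 80% with the cut | 81% | 96% | 16 points (80.9 to 96.5) |
| Five groups, 5 highest and 5 lowest | 51% | 56% | 4 to 5 points |
| Five groups, 5 highest and 5 lowest | 80% | 85% | 4 points |

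Placing the cut so that 30% rather than 50% respond changes little (80% v 96-97%; 49% v 78%). With extremes the loss is small because the label then tracks the titre closely.

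Within one group (n = 10, random 5+5) the loss depends heavily on r: 4% v 8% at r = 0.5, 11% v 32% at r = 0.7, 33% v 90% at r = 0.9.

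**4. The reverse case.** If expression jumps at the cut and is flat elsewhere, the pooled two-level term has 77% v 48% for the continuous term (random 5+5), or 76% v 71% (extremes).

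**5. Limits.** The simulation uses one mean per subject. It leaves out the two time points, the assumed within-subject correlation of 0.5 and the cell-level data, so it shows direction and rough size only.

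**The case against.** The case for the plan has five parts, and much of it stands.

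- **The documents never say response status is a cut of OPA.** This stands. A reader might infer that the plan dichotomises OPA, but the text supports only an omission: the promised analysis is not specified.
- **The Aim 3 model is introduced to compare fold-changes between groups, and Section 4.0 treats gene expression as a secondary endpoint for describing group differences.** True, and the model can serve that purpose. It does not supply the relation promised in Sections 1.0 and 2.0.
- **Response status defines the sampling and is the basis of the only stated Aim 3 power.** This stands, and is why a continuous term should not displace it.
- **A threshold relation favours the two-level term.** This stands, as step 4 shows.
- **Ten per group applies to the single-cell assay.** Section 1.0 also names flow cytometry for Aim 3, and Section 10.0 sets no subset limit on flow samples. If surface TNFR expression is measured in more people, the relation could be studied in more than 50. The figures above do not bound that analysis.

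**Conclusion.** The gap holds on the text alone: no specified analysis relates TNFR or gene expression to the OPA titre, although Sections 1.0 and 2.0 promise one and the titre is collected. It should be closed before analysis.

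The power cost is conditional. It requires that response status is an OPA cut and that the relation is roughly linear. The pooled, group-adjusted loss at alpha 0.005 is then about 15-30 points with random 5+5, where the cut has 50-80% power, and about 3-6 points with extremes. With a step at the cut the sign reverses.

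Two stronger readings are tempting and not supported. One is a single headline loss. The 57-point difference within one group needs r = 0.9, and the documents give neither r for expression nor the selection rule. The other is that the stated 80% power is unattainable. Without an SD, a responder definition or a selection rule, that cannot be shown.

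**What to change.** 1. Define responder: assay, serotype or serotypes, threshold and day. State how the 5+5 are chosen (at random within class, or extremes).
2. Keep the 5+5 sampling and the responder v non-responder contrast, with its stated power.
3. Add a prespecified mixed model of TNFR expression on continuous log day-30 OPA titre, adjusted for log day-0 titre (or on the log rise). Fit it by serotype or on the average of PPS14, 19A and 23F. Include group, time, the OPA-by-time interaction and the random subject effect. For Group 5 use days 366 and 396.
4. Report the slope with its 95% CI. Do not report a raw correlation from the response-selected sample, because the selection distorts it. Under a linear relation the slope is not biased by selection on OPA itself. If responders are chosen on another measure that is related to expression, that assurance is lost, which is a further reason for item 1.

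The cost is SAP wording and one more model to report, with no new participants, samples or assays. The added model has less power than the responder contrast if the true relation is a step, and the retained contrast covers that case.

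### The Aim 3 day 0 versus day 7 contrasts have no sample-level error term, so they are valid only if sample-to-sample variance is essentially zero

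*Combined protocol and SAP*

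**What the plan says.** The Aim 3 part of section 12.0 plans single-cell qPCR for TACI, BCMA and BAFF-R in 10 participants (5 responders, 5 non-responders) from each of 5 groups, at baseline and 7 days after vaccination. On the number of cells it says: "Each participant sample provides between 40-96 viable cells that will be evaluated for gene expression at the single cell level".

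The fixed part of the model is given as: "The model will include fixed effects for participant group, response status, and time". The random part is "a random subject effect to account for repeated measurements resulting from individual cells from the same subject samples". The use of the model is then stated: "Comparisons of number of gene expression between groups and within group between times will be evaluated using a series of contrasts from the LMM".

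For Aim 3 the section names no sample-level random effect, random slope for time, covariance structure, cluster-robust standard error, averaging of cells within a sample, or method for denominator degrees of freedom. The only variance input is a single within-subject correlation of 0.5, given in the power statement for responders versus non-responders (80% power for a 2.7 fold-increase or 0.60 fold-decrease, two-sided 0.005).

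**The concern.** The data have three levels: cell, sample (one subject on one day) and subject. The model has a variance term for the first and the last only. A subject intercept is common to both days, so it drops out of a day 0 versus day 7 difference. What remains as error is the cell-level residual.

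The resulting test is correct only if two cells from the same subject on different days are as alike as two cells from the same tube. Any real day-to-day variation in a subject's samples, biological or from processing, breaks that condition and makes the standard error too small. A stricter significance level does not repair an understated standard error. Ordinary sample-to-sample variation in TACI, BCMA or BAFF-R expression could then be reported as a change caused by the vaccine.

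The same random-subject wording works for Aims 1 and 2, where each outcome has one value per subject per time and the residual is itself the sample-level error. Aim 3 adds a layer of cells below the sample without adding the matching variance term.

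**Working it through.** **The plan's own figures.** The significance level reproduces: 0.05/10 = 0.005. The 2.7 and 0.60 fold-changes cannot be reproduced because no standard deviation of expression is given. They concern responders versus non-responders and are not the contrast at issue.

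**Inputs from section 12.0.** 5 groups of 10 subjects, 2 times, m = 40 or 96 cells per sample, correlation 0.5, two-sided 0.005. The plan attaches 0.005 to the responder comparison and states no level for the time contrasts, so 0.05 is shown too.

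**Assumed, because the documents do not give it.** Total variance is 1 and same-sample correlation is 0.5. The subject-by-time (sample) variance is s, the subject variance 0.5 − s and the cell variance 0.5. Values of s = 0, 0.01 and 0.05 are 0%, 1% and 5% of total variance, which makes the cross-day correlation 0.50, 0.49 and 0.45. The true change is zero.

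**Formulas.** For one group's time difference with n = 10:

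- True variance = (2/n)(s + 0.5/m).
- Variance the subject-only model reports = (2/n)(MS/m), with MS = [100(m − 1)(0.5) + f(0.5 + ms)] / [100(m − 1) + f]. The sample-level degrees of freedom pooled into the residual are f = 45 if group-by-time means are fitted, or f = 49 for the additive model as listed.
- R = true SE / reported SE = √[(s + 0.5/m) / (MS/m)].
- Type I error = 2Φ(−z/R), with z = 2.807 at 0.005 and 1.960 at 0.05.

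**One case in full (m = 40, s = 0.01, f = 45).** MS = [3900 × 0.5 + 45 × 0.9]/3945 = 1990.5/3945 = 0.5046. Then R = √(0.0225/0.012614) = 1.336, and the error is 2Φ(−2.807/1.336) = 0.0356.

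**Results (f = 45).**

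| Cells | s | R | Error at 0.005 | Error at 0.05 |
|---|---|---|---|---|
| 40 | 0 | 1.00 | 0.5% | 5% |
| 40 | 0.01 | 1.34 | 3.6% | 14% |
| 40 | 0.05 | 2.19 | 20% | 37% |
| 96 | 0 | 1.00 | 0.5% | 5% |
| 96 | 0.01 | 1.70 | 9.9% | 25% |
| 96 | 0.05 | 3.18 | 38% | 54% |

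With f = 49 the errors at 0.005 are 3.5% and 20% (40 cells) and 9.9% and 38% (96 cells), so the missing group-by-time term is not what drives the result.

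**Simulation.** With 40,000 trials per setting and f = 45, the errors at 0.005 for the three values of s were 0.48%, 3.6% and 19.5% (40 cells) and 0.49%, 9.9% and 37.8% (96 cells). In the same runs a paired t-test on sample means (9 df) gave 0.45–0.55%, and a test with sample-level error pooled over groups (45 df) gave 0.46–0.54%.

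**Degrees of freedom.** For one group fitted alone, the subject-only model claims 2 × 10 × 40 − 10 − 1 = 789 residual df (1909 with 96 cells). There are only 9 for its ten paired differences.

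**What is not affected.** Averaged over both times, between-group contrasts stayed at 0.42–0.51% and responder contrasts at 0.43–0.55%. The 5/5 responder selection is not a cause either: fixed, opposite changes of ±0.1 to ±0.3 with s = 0 gave 0.41–0.51%.

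**The case against.** The strongest reply is that the plan is under-specified and not wrong. A random subject effect does not literally exclude a random slope for time, and the phrase about cells from the same subject samples could be meant to cover clustering by sample. This stands to the extent that the finding depends on reading the term as an intercept. That is its ordinary meaning, however, and no slope or sample term appears anywhere for Aim 3.

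A second reply is that applying one correlation of 0.5 to cells at two times already assumes equal correlation within and across days. That is fair. It does so only implicitly, as a planning input for the responder comparison, and it is neither justified nor checked. The graphical checks in section 12.0 are written for Aims 1 and 2.

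Third, the size rests on assumed variances, and small ones do little. With 40 cells, s = 0.001 gives 0.69% at the 0.005 level or 5.9% at 0.05, and s = 0.002 gives 0.91% or 6.9%. With 96 cells, s = 0.001 already gives 1.0% or 7.3%. This stands: the actual inflation is unknown.

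Fourth, the stakes are narrow. Specific Aim 3 in section 1.0 is mainly a comparison between groups, and section 4.0 is descriptive in intent: "Secondary endpoint of the study is to describe differences in gene expression of 56 genes". This also stands and limits the weight of the point. The within-group time contrasts are nevertheless expressly planned.

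**Conclusion.** The concern holds. With the subject effect read as a random intercept, the Aim 3 within-group time contrasts have standard errors that are too small unless subject-by-time variance is essentially zero. The algebra does not depend on any assumed figure; the size does. At an assumed 1% to 5% of total variance the true standard error is 1.34 to 2.19 times the reported one with 40 cells, and 1.70 to 3.18 times with 96. More cells make the distortion worse because they shrink only the error the model recognises. The problem is confined to these secondary time contrasts. It leaves the printed power statement and the time-averaged group and responder contrasts materially intact. It should be corrected, but it does not threaten the study's primary results.

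**What to change.** In the Aim 3 part of section 12.0, add a random subject-by-time (sample) effect to the model and name Satterthwaite or Kenward-Roger degrees of freedom. Alternatively, reduce each sample to its mean log expression and analyse paired subject-level changes. State which is used, and state the significance level for the time contrasts. If a random slope for time was intended all along, say so.

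The cost is one variance component and about one sentence of text, with no new data. The downside is wider intervals and less power for the time contrasts. If the sample-level variance is truly zero, that precision is lost for nothing. The ratio of critical values gives the size of the loss:

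- At 0.005, intervals are 1.05 times as wide with pooled sample-level error (45 df), or 1.31 times with a paired t per group (9 df).
- At 0.05, the ratios are 1.03 and 1.15.

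With 40 cells, zero sample variance and a paired t at 0.005, the difference detectable with 80% power rises from 0.26 to 0.33 cell-level standard deviations.

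### The Aim 3 power statement gives 80% power to a 2.7 fold-increase and to a 0.60 fold-decrease, which do not pair on the log or raw scale with a common SD; no SD or scale is stated

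*Combined protocol and SAP*

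**What the plan says.** The Aim 3 part of section 12.0 (Data Management) plans single-cell qPCR of TNFR markers in 10 participants from each of the five groups, half responders and half non-responders, at baseline and day 7. The outcome is relative fold-change in expression, analysed with a linear mixed model.

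The power claim concerns responders against non-responders within a group:

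- Size: "a sample size of 5 responders and 5 non-responders", each with at least 40 "cell level measures at 2 time points".
- Test: "using a two-sided test assuming within subject correlation of 0.5", and a "Bonferroni corrected significance level (up to 10 comparisons) of $p = 0.005".
- Result: the design is credited with "80% power to detect 2.7 fold-increase or a 0.60 fold-decrease in expression using a two-sided test".

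For comparisons between groups, the paragraph says only that 10 subjects per group will make still smaller fold-changes detectable. It gives no figure.

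The paragraph states no SD or variance component, does not name the scale on which expression is analysed, and does not say whether 0.60 is the ratio that remains or the size of the reduction. The only remark on transformation in section 12.0 belongs to Aims 1 and 2, where it is left open until the model assumptions have been checked.

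**The concern.** One design, one significance level and one power are attached to two effects. A two-sided test with a common SD has limits that are symmetric on the scale of analysis. For a relative fold-change analysed on the log scale, the detectable decrease is therefore the reciprocal of the detectable increase. The reciprocal of 2.7 is 0.37, which is neither 0.60 nor 0.40 (the ratio left after a 60% reduction).

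What is at stake is what a reader takes the Aim 3 subset to be capable of. The two readings of 0.60 describe very different sensitivities, and the between-group claim has no other support than this sentence. Without an SD, nobody can check the 80% or decide which of the two figures to rely on.

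**Working it through.** **Inputs, all from the Aim 3 paragraph of section 12.0.** 5 against 5 subjects; two-sided alpha 0.005; power 80%; effects 2.7 up and 0.60 down; within-subject correlation 0.5; at least 40 cells at each of 2 time points. SD and scale: not given.

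**Step 1: the plan's own figures.** The significance level reproduces: 0.05/10 = 0.005. The 80% cannot be reproduced, because no SD is stated. What can be tested is whether the two effects are consistent with each other.

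**Step 2: distances from no change.**

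| Effect | Ratio | ln(ratio) | Raw change | Log-scale partner |
|---|---|---|---|---|
| 2.7 fold-increase | 2.7 | +0.993 | +1.7 | 1/2.7 = 0.37 (63% reduction) |
| 0.60 read as a ratio | 0.60 | −0.511 | −0.4 | 1/0.60 = 1.67-fold increase |
| 0.60 read as a reduction | 0.40 | −0.916 | −0.6 | 1/0.40 = 2.5-fold increase |

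Rounding of 2.7 does not close the gap: 2.65 to 2.75 gives partners of 0.38 to 0.36, that is, reductions of 62% to 64%.

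**Step 3: power of one effect, given the other (log scale, common SD).** The noncentrality is proportional to |ln(ratio)|. The SD, the correlation and the cell count enter both effects in the same way and cancel.

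- Noncentrality needed for 80% power at two-sided 0.005: normal approximation 2.807 + 0.842 = 3.649; t test with 8 df, 4.866.
- Ratio 0.60: 0.511/0.993 = 0.514. Noncentrality 3.649 × 0.514 = 1.876 (normal) or 4.866 × 0.514 = 2.503 (t). Power 17.6% or 19.0%.
- Ratio 0.40: 0.916/0.993 = 0.923. Noncentrality 3.366 or 4.489. Power 71.2% or 71.7%.
- Reversed, with 80% assigned to a ratio of 0.60: noncentrality for 2.7 is 3.649/0.514 = 7.09 or 4.866/0.514 = 9.46. Power nearly 100%.
- Reversed, with 80% assigned to a ratio of 0.40: 2.7 has about 87%.

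**Step 4: raw scale, common SD.** With 80% at a change of 1.7, a change of 0.4 has about 3% power (0.4/1.7 = 0.235 of the noncentrality) and a change of 0.6 about 6–7% (0.353).

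**Step 5: the SD each figure would need.** With n = 5 per arm, the SD of a subject's mean log expression is |ln(ratio)| / (noncentrality × √(2/5)).

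- For 2.7: 0.993/(3.649 × 0.632) = 0.43 (normal) or 0.993/(4.866 × 0.632) = 0.32 (t).
- For a ratio of 0.60: 0.22 or 0.17.
- For a ratio of 0.40: 0.40 or 0.30.

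The 2.7 and the ratio of 0.60 thus imply SDs that differ by a factor of about two, and the plan supports neither.

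**Step 6: the between-group statement.** If 2.7 has 80% at 5 against 5, then 10 against 10 with the same SD multiplies the noncentrality by √2. A ratio of 0.60 then has about 44% power (normal, noncentrality 2.65) to 63% (t with 18 df, noncentrality 3.54). A ratio of 0.40 has 97% to above 99%. These figures carry the same condition as Step 3.

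**The case against.** Five arguments can be made for the plan.

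1. **The scale is not stated, so reciprocity is not forced.** This stands in part. The effects come close on the reciprocal scale (0.630 against 0.667) and are equal under a power transform with exponent near −0.92, so it would be wrong to say that they disagree on every scale. But the plan names no such transform, and on the log and raw scales they disagree under either reading of 0.60.

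2. **A 0.60 fold-decrease may mean a 60% reduction.** This stands as a possibility. The gap is then 60% against 63%, or about 72% against 80% power, and may be loose rounding. The text does not say that this is meant.

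3. **80% may mean at least 80%.** This stands. An SD small enough for a ratio of 0.60 gives 2.7 nearly full power, and neither effect is underpowered. The sentence then presents as a limit a figure that is not one.

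4. **The figure does not concern the main hypothesis.** A reader might infer that Aim 3 has only 18–19% power for the reduced TNFR expression postulated in transplant recipients. The documents do not support that. The sentence covers responders against non-responders at 5 against 5; the postulated deficit concerns transplant recipients against controls, with 10 per group. Nor does the plan say whether responders or non-responders are the reference, so a deficit in one can equally be written as an increase in the other. The 18–19% also holds only if 2.7 is the correct figure.

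5. **Gene expression is a secondary endpoint** (section 4.0), measured in a subset, and no analysis rule depends on this sentence. This is true, and it limits the weight of the point.

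**Conclusion.** The power sentence is internally inconsistent. With a common SD, a 2.7 fold-increase and a 0.60 fold-decrease cannot both sit at exactly 80% power on the log or the raw scale. The size depends on the reading and on which figure is trusted. With 2.7 fixed at 80%, a ratio of 0.60 has about 18–19% and a ratio of 0.40 about 71–72%; with a ratio of 0.60 fixed at 80%, 2.7 has nearly 100%.

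The documents do not show which figure is wrong, because they give neither SD nor scale. That omission is the firmer part of the defect: it makes the 80% uncheckable whichever way 0.60 is read. The conclusion rests on a common SD and on a log or raw analysis. It does not establish that the design is too weak for the study's hypothesis. It does establish that the stated limits need to be recomputed before anyone relies on them.

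**What to change.** In the Aim 3 paragraph of section 12.0:

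- State that expression is analysed on the log scale, if that is intended, and give the assumed log-scale SD with its between-subject and within-subject parts and its source.
- Recompute both limits from that SD and state them as reciprocals. If 2.7 stands, the matching decrease is a ratio of 0.37, that is, a 63% reduction. If the decrease is the figure that stands, change the increase instead: 1.67-fold for a ratio of 0.60, or 2.5-fold for a ratio of 0.40.
- Say whether a fold-decrease is the remaining ratio or the proportion lost.
- Replace the general remark on between-group comparisons with detectable limits for 10 per group, computed from the same SD.

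If another scale is intended, name it and show that both limits follow from one SD on that scale. The cost is one corrected sentence, with the between-group remark brought into line, and possibly a less favourable detectable decrease. Nothing in the design or data collection has to change.
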